6 VARIABLES AND EPIDEMIOLOGICAL MEASUREMENTS

6.1 Patient Characteristics

The following information will be obtained at Baseline:

- Demographic variables (as allowed by local regulations):
 - Age
 - Date of data collection
 - Sex
- Current physiological variables:
 - Height (inches)
 - Weight (pounds)
 - Temperature
 - Blood pressure
 - Heart rate (beats per minute)

- Respiratory rate
- Oxygen saturation (pulse oximetry)
- Pulmonary function tests including: FEV₁, FVC, FEV₁/FVC ratio: obstructive versus restrictive, and peak expiratory flow (PEF)
- Comfort and familiarity with technology, including, but not limited to, internet use, ownership of smartphones, email use, etc.
- Relevant concomitant medications including, but not limited to, respiratory medications
- Abbreviated medical history (from birth to Baseline visit)
- Relevant previous respiratory medical history or procedures including, but not limited to, thoracentesis, subsequent radiation, etc.
- Disease characteristics, such as date of diagnosis, stage at diagnosis, current stage, etc.
- Previous treatments for NSCLC, including sequential CRT, cCRT regimen for unresectable Stage III NSCLC
- Time since most recent radiation

6.2 Exposure and Covariates

The primary exposure for this study will be multiparametric mobile technology in patients with unresectable Stage III NSCLC receiving durvalumab. As part of the inclusion criteria, patients may initiate durvalumab treatment within 2 weeks of Baseline. The decision to prescribe durvalumab will be made before enrollment, based on physician recommendation. The site physician or qualified site personnel will discuss the study with the patient after agreement to initiate durvalumab treatment, and the patient will be enrolled after consent and evaluation of eligibility using inclusion/exclusion criteria.

7 STUDY CONDUCT

7.1.1 Enrollment

Patients who are potentially eligible for enrollment will be contacted by qualified site personnel to gauge their interest in joining the study. Interested patients will be screened during their routine care visit, at which time they will be able to ask questions.

After explanation of the study by qualified site personnel, patients wishing to join the study will be asked to sign a study-specific ICF. Baseline information about the patient, including demographic data, relevant treatment and medical history, height, weight, vital signs (temperature, heart rate, respiratory rate, and blood pressure), oxygen saturation (pulse oximetry), pulmonary function (spirometry), and QoL measurements at time of visit, will be collected.

All patients enrolled will continue to receive routine standard of care treatment for NSCLC as per their treating physician's discretion. All patients will receive appropriate training on the devices and tablet application used in the Current Wearable Health Monitoring System. Patients will receive technology for home use and will otherwise continue to receive routine standard of care treatment for NSCLC as per their treating physician's discretion. Each site will be provided with appropriate training materials and support.

7.1.2 Study Period

All patients enrolled will be followed up to 12 months on durvalumab or until confirmed disease progression, permanent discontinuation of durvalumab treatment, the initiation of alternative cancer therapy, unacceptable toxic events, death, or withdrawal of consent, whichever is sooner.

At the End-of-Study visit (after 12 months of durvalumab dosing or upon withdrawal/discontinuation), information about the patient including height, weight, vital signs (temperature, heart rate, respiratory rate, and blood pressure), oxygen saturation, pulmonary-related concomitant medications and procedures, and information on AEs/SAEs (including pneumonitis), will be collected. The patient will also be prompted to take the QoL and **CCI**

A patient is considered to have completed the study when he/she has provided multiparametric data using the devices and installed application on a tablet in the Current Wearable Health Monitoring System through 12 months (or 26 cycles) of durvalumab treatment. In certain cases, a patient who does not complete all 26 cycles (i.e., durvalumab treatment prematurely discontinued due to an immune-related AE) may still be considered a study completer.

The end of study is defined as the date the last expected data will be collected.

7.1.3 Technical and Patient Support

This study uses connected devices that will be paired to a mobile application which needs to be installed on a tablet or smart phone. Site personnel will be suitably trained on the Current Wearable Health Monitoring System to onboard patients with all technology and study procedures. Designated site personnel will help the patients pair all connected devices, and train patients on how to use each connected device and the tablet application. Patients will be

asked to contact the study site for issues related to study procedures or for technical support. The study site will facilitate connection with the Current Health Call Center for assistance, as necessary. For medical questions or to report AE signs/symptoms, patients will be asked to contact their treating physicians directly.

7.1.4 Patient Compensation

To recognize the significant time commitment the patients will make in completing daily tasks, patients will be compensated for their participation in the study. Patients who enroll in the study will be compensated for successfully completing the Day 1 Baseline visit and for each successful week on the study.

7.2 Data Management

For this study Cisiv's Baseline Plus database platform will be used (Cisiv Baseline Plus).

Baseline Plus will be used to capture data from a patient's medical records. The Current Wearable Health Monitoring System will capture the symptomatic and specific device data from the patients. This data will be combined with the data in the Baseline Plus database at the end of the study.

High quality data standards will be maintained, and processes and procedures will be used to ensure that the data are as clean and accurate as possible when presented for analysis. Data quality will be enhanced through a series of programmed data quality checks that automatically detect missing or anomalous data. All the modifications to the data will be recorded in an audit trail.

7.3 Data Collection Plan

The data collection plan presented in [Table 1](#) outlines all data points that will be obtained from patients' medical records, mobile devices, and QoL questionnaires, as collected in the tablet application, in the study. All patients in the study will attend routine visits, as recommended by the treating physician.

Table 1 Data Collection Plan for All Patients

Variables	Baseline (Day 1)	Daily Data Collection via Current Wearable Health Monitoring System	Data Collection via a Tablet Every 2 Weeks for First 3 Months and Once Monthly Thereafter	Standard of Care Visits	End-of-Study Visit	Safety Follow-Up (End-of-Study Visit +30 days)
Demographics: Age, gender; height	x					
Weight	x			x	x	
Blood pressure	x			x	x	
Vital Signs (temperature, heart rate, respiratory rate)	x	x		x	x	
NSCLC treatment and disease history, including time of most recent radiation	x					
Relevant medical and surgical history	x					
Pulmonary-related concomitant medication and procedures ^a	x			x	x	
All AEs/SAEs (including durvalumab-related and device-related AEs) ^b	x			x	x	x
If pneumonia or pneumonitis is diagnosed, details on pneumonitis and radiation pneumonitis if applicable	x			x	x	x
Quality of life questionnaires: EORTC QLQ C30, EORTC QLQ LC13	x		x		x	
CCI [REDACTED]					CC	
Lung function measurements spirometry: FEV ₁ , FVC, FEV ₁ /FVC ratio, and PEF	x	x			x	
Pulse oximetry – oxygen saturation	x	x			x	
Activity step count		x				
Training on Current Wearable Health Monitoring System	x					
Durvalumab treatment ^c	x			x	x	

AE = adverse event; EORTC QLQ C30 = European Organization for Research and Treatment of Cancer Quality of Life Core Questionnaire; EORTC QLQ LC13 = European Organization for Research and Treatment of Cancer Quality of Life Lung Cancer Module; FEV₁ = forced expiratory volume; FVC = forced vital capacity; NSCLC = non-small cell lung cancer; PEF = peak expiratory flow

^a Information regarding concomitant medication (including over-the-counter medications) will include, when available: drug name, indication for treatment, route, and duration of drug administration.

^b Adverse event collection (including event description, intensity/severity, outcome, action taken, etc.) will occur at Baseline (i.e., after the patient signs the ICF), during standard of care visits, at the End-of-Study visit, and for 30 days after the End-of-Study visit to capture late-onset symptoms.

^c Information regarding durvalumab treatment will include, when available: start/stop date, treatment holds, interruptions, and/or permanent discontinuations (including reasons), as well as details of other treatments (ie, chemotherapy, radiation therapy, etc).

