3.2 Study Endpoints

The endpoint used to address the primary objective is:

- Occurrence of pneumonitis (either radiation or immune-mediated, by grade).
 - Grade of pneumonitis at diagnosis and highest grade of pneumonitis

The endpoints used to address the secondary objectives are:

- Occurrence of pulmonary AEs, including diagnoses of events, by grade
- Duration (days) of pulmonary AEs by type and grade
- Permanent discontinuation of durvalumab due to pulmonary AEs, including pneumonitis
- Early discontinuation of durvalumab treatment for any reason
- Duration (days) of durvalumab treatment
- Treatment interruptions, duration (days) of interruptions, and the reason for interruptions that will be captured in a standard data management form with the site physician documenting reasons in patient charts
- Time (days) to development of Grade 3 to 5 AEs, including pneumonitis

- Prescription of medication used to manage pulmonary AEs and duration (days) of treatment
- Change in QoL scores from baseline

The endpoints used to address the exploratory objectives are:

CCI

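### Pulmonary medication is not scheduled for collection after the End-of-Study visit, although pneumonitis is followed 30 days longer, so the medication-duration endpoint is incomplete mainly in cases that end durvalumab

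*Protocol*

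**What the plan says.** **Follow-up and the closing visit.** Protocol 7.1.2 states: "All patients enrolled will be followed up to 12 months on durvalumab or until confirmed disease progression, permanent discontinuation of durvalumab treatment", along with other stopping events. The same section times the last visit as follows: "At the End-of-Study visit (after 12 months of durvalumab dosing or upon withdrawal/discontinuation". It gives no number of days within which that visit must take place after discontinuation. Pulmonary-related medication is among the items it lists for that visit.

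**Collection schedule.** In Table 1 of Protocol 7.3:

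- The row "Pulmonary-related concomitant medication and procedures" is marked at Baseline, Standard of Care visits and the End-of-Study visit. Its Safety Follow-Up cell is blank.
- The row for all AEs and SAEs, and the row "If pneumonia or pneumonitis is diagnosed, details on pneumonitis and radiation pneumonitis if applicable", carry marks at the same three points and also at Safety Follow-Up.
- Footnote b explains that AE collection continues "for 30 days after the End-of-Study visit to capture late-onset symptoms".
- Footnote a asks that the medication record hold, when available, "drug name, indication for treatment, route, and duration of drug administration".

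**Endpoint.** Protocol 3.2 and SAP 3.3 both name as a secondary endpoint: "Prescription of medication used to manage pulmonary AEs and duration (days) of treatment".

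**Analysis.** SAP 4.2.2.8 refers this endpoint to SAP 4.2.4.5, which tabulates medications by ATC class and generic name and provides a listing. It contains no formula for duration and no censoring rule. SAP 3.2 does not impute an end date for ongoing medication. SAP 4.2.2.2, by contrast, censors AE duration at death or study exit and uses Kaplan-Meier.

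**The concern.** A pneumonitis that leads to permanent discontinuation also triggers the last visit at which its medication is scheduled to be recorded. Collection of the treatment data then stops while collection of the event goes on. Two kinds of record are affected:

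- a course still running at the End-of-Study visit has a start date but no scheduled stop date;
- medication first started in the following 30 days has no scheduled record, even though the event it treats may be captured.

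The loss is not random. It depends on the event under study, and it falls mainly on patients whose event ended treatment. A description of how long pulmonary events needed medication would then rest on shorter or open-ended records in the cases where the question matters most.

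**Working it through.** **The plan's own figure.** The only computed design figure is Table 4 in Protocol 9.1. All 12 exact Clopper-Pearson intervals for n = 75 reproduce to one decimal (for example, 0 events gives 0.0% to 4.8%). The point here does not depend on them.

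**Step 1. Scheduled collection, side by side.**

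| Table 1 row | Baseline | Standard of Care | End-of-Study | Safety Follow-Up (+30 days) |
|---|---|---|---|---|
| Pulmonary medication and procedures | x | x | x | blank |
| AEs/SAEs | x | x | x | x |
| Pneumonitis details | x | x | x | x |

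**Step 2. Other text that might fill the blank cell.**

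- Protocol 7.4.6 says concomitant medication details are collected, but sets no schedule after the End-of-Study visit.
- Protocol 8.3.1.3 lists the AE fields. Its action field concerns durvalumab, and no field covers medication given for the event.
- Protocol 8.3.1.4 lets the investigator authorise further follow-up of an unresolved AE. That is discretionary and does not mention medication.
- The clause in 7.1.2 that lets some patients who stop early count as completers changes their status, not what is collected.

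None of these schedules medication collection after the visit.

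**Step 3. How many patients.** Inputs are n = 75 (Protocol 9.1) and the durvalumab-arm discontinuation rates from the Phase 3 trial cited in Protocol 2.2: 4.8% for pneumonitis and 1.3% for radiation pneumonitis.

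- Pneumonitis alone: 75 × 0.048 = 3.6 patients.
- Both, assuming no overlap: 75 × (0.048 + 0.013) = 75 × 0.061 = 4.6 patients.
- At 6.1%, the central 95% binomial range is 1 to 9 patients, and the chance of at least one is 0.99. At 4.8% that chance is 0.975.
- Share of expected pneumonitis: at the 33.9% any-grade rate, 75 × 0.339 = 25.4 cases, and 0.061 / 0.339 = 18%.

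These are patients in whom the gap can arise. It arises only if medication is still running at the visit or starts after it.

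**Step 4. Days lost.** These cannot be computed from the documents. As an illustration only, let L be the course length and g the days from medication start to the End-of-Study visit, both assumed. Days on record are min(L, g + 1) under the present table and min(L, g + 31) if collection also covered Safety Follow-Up.

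| Assumed g | Assumed L | On record now | With +30 days |
|---|---|---|---|
| 7 | 28 | 8 | 28 |
| 7 | 84 | 8 | 38 |
| 14 | 28 | 15 | 28 |
| 14 | 84 | 15 | 45 |
| 30 | 28 | 28 | 28 |

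With g of 7 to 14 days and L of 28 to 84 days, the share on record now runs from 8/84 = 10% to 15/28 = 54%. The last row shows that nothing is lost when a course ends before the visit. The 84-day rows show that 30 more days do not complete a long course.

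**The case against.** The best defence is that a blank cell does not prove that nothing will be recorded. Section 7.4.6 states no cut-off, and its preceding paragraph refers to the whole study. The content of the pneumonitis details is not itemised. Footnote b includes action taken among the AE items. SAP 3.2 shows that the CRF links medications to AEs and allows some missing dates to be imputed through that link. Clinical data come from medical records, so some stop dates may be found. This makes it wrong to say that no treatment will be captured. It does not supply a schedule, and 7.3 presents Table 1 as the full outline of data points.

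A second defence is that the protocol's definition of a treatment-emergent AE (8.3.1.1) also ends at the End-of-Study visit, so the medication cut-off matches it. That is correct. However, Table 1 deliberately collects events beyond that visit. SAP 4.2.4.8 extends the treatment-emergent window to 30 days after the last dose, and SAP 4.2.1 sets no upper time limit on pneumonitis. An event in the window can therefore be analysed with no planned medication record.

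Third, the SAP plans no summary of medication duration, so the gap biases no planned statistic. This stands, and it means the SAP needs a change as well.

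A reader might also infer that nearly all durations in severe cases are cut off. The documents do not support that. Protocol 2.2 does not report discontinuation by grade, and nothing says treatment is usually still running at the visit. A hold may precede permanent discontinuation (SAP 4.2.2.6 allows for this), with medication recorded at standard-of-care visits meanwhile.

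**Conclusion.** The mismatch in Table 1 is real, and no other text closes it. As scheduled, stop dates are missing for pulmonary medication still running at the End-of-Study visit, and medication first started in the next 30 days is missing altogether. The secondary endpoint is incomplete, chiefly in treatment-ending cases.

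About 3.6 to 4.6 of 75 patients would be in the group at risk. This assumes that the cited trial's rates carry over and, for the upper figure, that the two rates add without overlap. The number of days lost is unknown.

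It would go too far to conclude that every course for a treatment-ending pneumonitis is cut off, or that analysis can do nothing. Courses finished before the visit are complete, and ongoing courses keep their start dates and can be censored. What analysis cannot restore is an unrecorded stop date or an unrecorded new course.

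This is one secondary endpoint in a descriptive pilot without formal testing. It is worth correcting because the correction is small and the missing records are tied to the outcome.

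**What to change.** **Protocol.** In Table 1, mark "Pulmonary-related concomitant medication and procedures" at Safety Follow-Up. Add matching text in 7.4.6 or 8.3.1.3 so that start and stop dates are recorded, over the same period as the event, for medication given for a pulmonary AE or pneumonitis.

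**SAP.** In 4.2.2.8 and 4.2.4.5, define medication duration from its start and stop dates, and censor courses still ongoing at last contact, in the way 4.2.2.2 treats AE duration. State whether study exit means the End-of-Study visit or the Safety Follow-Up, since the censoring date depends on it. The table mark alone would leave the endpoint without a defined analysis.

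**Cost.** One table mark and a small amount of extra data entry at a contact that already records AEs and pneumonitis details. Courses running beyond the 30 days remain censored. The change concerns data collection and analysis only and leaves clinical management as it is.

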7.4 Study Procedures

7.4.1 Medical Devices

The medical device provided for use in this study is the Current Wearable Health Monitoring System.

- Manufacturer: Current Health Ltd.

The product codes associated with FDA authorization of the device are shown in Table 2.

Table 2 Product Codes associated with the Current Wearable Health Monitoring System

BZG	Spirometer, Diagnostic
BZQ	Monitor, Breathing Frequency
DQA	Oximeter
DRG	Transmitters And Receivers, Physiological Signal, Radiofrequency
MSX	System, Network And Communication, Physiological Monitors
FLL	Thermometer, Electronic, Clinical

Patients enrolled in the study will use the following electronic devices:

- Spirometer (Spirobank G as part of the Current Wearable Health Monitoring System)
- Multiparametric wearable device (as part of the Current Wearable Health Monitoring system)
- Tablet (application installed on tablet is part of the Current Wearable Health Monitoring system)

The Current Wearable Health Monitoring System is intended for:

- Continuous monitoring of the following parameters in adults:
 - Pulse rate (*Multiparametric wearable device*)
 - Oxygen saturation (*Multiparametric wearable device*)
 - Skin temperature (*Multiparametric wearable device*)
 - Movement (*Multiparametric wearable device*)
- Intermittent monitoring in adults of:
 - Respiration rate (*Multiparametric wearable device*)
 - Lung function & spirometry (*Spirobank G Spirometer*)
 - Non-invasive blood pressure (*feature not used in this study*)
 - Weight (*feature not used in this study*)

Training for the patients on the above devices and application will be provided by the investigative site personnel. Qualified site personnel as identified by the PI will review data collected by the devices once daily during business hours (exempting office closures, such as holidays, weekends, etc.), and will contact patients if a clinical intervention is necessary or if there are other issues related to study procedures. However, patients will be advised to contact their treating physicians directly if they are experiencing new or worsening of existing AE-related-symptoms. Technical support will be provided by the study site and Current Health Call Center as described in [Section 7.1.3](#).

7.4.2 Symptom Assessments

Pulmonary function data collected via mobile applications and devices are described in Table 3.

Table 3 Data Collected via the Current Wearable Health Monitoring System

Pulmonary Function Parameters	Lowest Acceptable Value*
FEV ₁	LLN
FVC	LLN
FEV ₁ /FVC ratio	LLN
Oxygen saturation	90%
PEF	LLN

FEV₁ = forced expiratory volume; FVC = forced vital capacity; LLN = lower limit of normal; PEF = peak expiratory flow

* Measurements less than the LLN indicate the presence of an abnormality

Study physicians should review values lower than normal on a daily basis in alignment with regular business hours (as noted above) and patients will be contacted if clinical intervention is necessary.

Patients will be advised to contact their treating physicians if they develop any of the following symptoms from either a change of baseline or a new worsening symptom that needs to be reported as a potential AE/serious adverse event (SAE): trouble breathing, chest pain, new or worsening cough, productive cough with purulent secretions, shortness of breath, fever, or tachycardia.

7.4.3 Quality of Life Assessment Questionnaires

Patients in the study will fill out QoL assessments using the European Organization for Research and Treatment of Cancer Quality of Life Core Questionnaire (EORTC QLQ C30) and the Lung Cancer Module (EORTC QLQ LC13) at the baseline visit prior to treatment being administered, at home every 2 weeks for the first 3 months and once monthly thereafter, and at their End-of-Study visit.

7.4.4 CCI [REDACTED]

CCI [REDACTED]
[REDACTED]
[REDACTED]
[REDACTED]
[REDACTED]
[REDACTED]

7.4.5 NSCLC Disease History/Respiratory Disease History

On Day 1, the patients' NSCLC disease history will be collected, including date of diagnosis, stage at diagnosis, and treatment history (including date of most recent radiation).

7.4.6 Durvalumab Treatment

Throughout the study, updated information on the patients' durvalumab treatment will be collected, including durvalumab start and stop date, treatment holds, interruptions, and permanent discontinuations (including reasons for each), as well as details regarding other treatments such as chemotherapy and radiation therapy (including doses and number of cycles).

Concomitant medication (including over-the-counter medication) details will also be collected. The indication for treatment must be recorded, including drug name, route, and duration of drug administration.

